## 6.11. Analysis for other secondary objectives

These analyses will be performed only on children enrolled in the AS ATP cohort for each group (6-12 weeks and 5-17 months).

### 6.11.1. Analysis population

Primary analysis will be performed on the other secondary endpoints (i.e. malaria, anaemia, hospitalisation and death as described in Table 4) at one year post last dose of the primary schedule in order to anticipate further comparisons to be done with the EPI-MAL-003 study (i.e. indirect, total and overall effects computation):

- D3 → D3 + 1Y: one year after the third dose (before 12 months of age) of EPI vaccine or virtual vaccination evaluated from third dose.

Additional analyses will be performed on the other endpoints:

- D3 → D4 + 1Y: one year after the visit mimicking the 4th dose (i.e. Month 32) evaluated from the 3rd dose (before 12 months of age) of EPI vaccine or virtual vaccination.
- D3 → D3 + 2Y: two years after the 3rd dose of EPI vaccine or virtual vaccination evaluated from 3rd dose of EPI vaccine or virtual vaccination

- D1 → D4 + 2Y: two years after the visit mimicking the 4th dose (i.e. Month 44) evaluated from the 1st dose of EPI vaccine or virtual vaccination
- D3 → D4 + 2Y: two years after the visit mimicking the 4th dose (i.e. Month 44) evaluated from the 3rd dose of EPI vaccine or virtual vaccination.

### 6.11.2. Derivation of incidence rate and prevalence

- For all endpoints listed in **Table 4** incidence rate will be calculated by dividing the number of all cases over the follow-up period by person-year as defined in the table.

If a subject had several cases during the period defined, all episodes will be reported.

The number of person-years will be computed as the sum of subjects follow-up period expressed in years.

**Table 3** Follow-up period definition for other secondary endpoints

Analysis	Start	Stop (earliest)
D3 → D3 + 1Y	Third dose or virtual vaccination*	
 
• One year after third dose
 
• Date of death
 
• Date of last contact**
 
• Date of migration
 
• Date when child reaches 5 years
 

D3 → D4 + 1Y	Third dose or virtual vaccination*	
 
• One year after virtual fourth dose
 
• Date of death
 
• Date of last contact**
 
• Date of migration
 
• Date when child reaches 5 years
 

D3 → D3 + 2Y	Third or virtual vaccination*	
 
• Two years after third dose
 
• Date of death
 
• Date of last contact**
 
• Date of migration
 
• Date when child reaches 5 years
 

D1 → D4 + 2Y	First dose or virtual vaccination*	
 
• Two years after virtual fourth dose
 
• Date of death
 
• Date of last contact**
 
• Date of migration
 
• Date when child reaches 5 years
 

D3 → D4 + 2Y	Third dose or virtual vaccination*	
 
• Two years after virtual fourth dose
 
• Date of death
 
• Date of last contact**
 
• Date of migration
 
• Date when child reaches 5 years
 

\* Virtual vaccination: for 5-17 month study group or unvaccinated children

\*\* Date of last contact: lost-to follow-up

The prevalence rate for anaemia will be computed by dividing the number of all cases by the number of enrolled children.

**Table 4 Incidence rate and prevalence calculations for other secondary objectives (children enrolled in active surveillance)**

Endpoints	Numerator	Denominator
Any malaria	# cases of any malaria during the follow-up time of each analysis Source: Outpatient visits and hospitalisations at all health care facilities	Person-years contribution of enrolled children during the follow-up time of each analysis
Any P. falciparum malaria	# cases of any malaria due to P. falciparum during the follow-up time of each analysis Source: Outpatient visits and hospitalisations at all health care facilities	Person-years contribution of enrolled children during the follow-up time of each analysis
Severe malaria	# cases of severe malaria during the follow-up time of each analysis Source: Outpatient visits and hospitalisations at all health care facilities	Person-years contribution of enrolled children during the follow-up time of each analysis
Severe P. falciparum malaria	# cases of severe malaria due to P. falciparum during the follow-up time of each analysis Source: Outpatient visits and hospitalisations at all health care facilities	Person-years contribution of enrolled children during the follow-up time of each analysis
Cerebral malaria	# cases of cerebral malaria during the follow-up time of each analysis Source: Hospitalisations	Person-years contribution of enrolled children during the follow-up time of each analysis
Death – all cause	# deaths (due to any cause) during the follow-up time of each analysis Source: Regular home visits; outpatient visits and hospitalisations at all health care facilities, completion visit; HDSS register	Person-years contribution of enrolled children during the follow-up time of each analysis
Malaria attributed deaths	# cases of deaths with malaria listed as a contributing cause during the follow-up time of each analysis Source: Regular home visits; outpatient visits and hospitalisations at all health care facilities, completion visit; HDSS register	Person-years contribution of enrolled children during the follow-up time of each analysis
P. falciparum Malaria attributed deaths	# cases of deaths with malaria due to P. falciparum listed as a contributing cause during the follow-up time of each analysis Source: Regular home visits; outpatient visits and hospitalisations at all health care facilities, completion visit; HDSS register	Person-years contribution of enrolled children during the follow-up time of each analysis
All cause hospitalisation	# of children hospitalised during the follow-up time of each analysis Source: Hospitalisations	Person-years contribution of enrolled children during the follow-up time of each analysis
Malaria attributable hospitalisation	# of children hospitalised during the follow-up time of each analysis where malaria is listed as the primary diagnosis Source: Hospitalisations	Person-years contribution of enrolled children during the follow-up time of each analysis
P. falciparum Malaria attributable hospitalisation	# of children hospitalised during the follow-up time of each analysis where P. falciparum malaria is listed as the primary diagnosis Source: Hospitalisations	Person-years contribution of enrolled children during the follow-up time of each analysis
Anaemia in hospitalised children	# cases of anaemia Source: Hospitalisations	Number of enrolled children
Severe anaemia in hospitalised children	# cases of severe anaemia Source: Hospitalisations	Number of enrolled children

As done for safety endpoints, analysis of risk factors will be conducted by means of univariate and multivariable Poisson regression models for ***any malaria, severe malaria and cerebral malaria***. The methods are described in Section 7.5.1. The covariates and their select method are described in Section 7.5.3.

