9.2.7.2.10. Record diagnosis

Record main diagnosis and any secondary diagnoses made by the physicians in the eCRF.

CONFIDENTIAL115055 (EPI-MALARIA-002 VS AME)
Protocol Amendment 7 Final**9.2.7.2.11. Record haemoglobin measurement**

For all hospitalised subjects, measurement of haemoglobin concentration, if available, at hospital entry will be recorded in the eCRF.

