Follow-up children up to study conclusion, by a check-up at the hospital 1 month, 6 months and 1 year after hospital discharge	•	
Only for subjects with suspected malaria		
For suspected malaria, record malaria microscopy and/or RDT or other result	•	
Study conclusion		•

Hospitalisation visits: subjects aged < 5 years, to include subjects referred in between active surveillance visits.

- is used to indicate a study procedure that requires documentation in the individual eCRF
- is used to indicate a study procedure that does not require documentation in the eCRF

1. See [Annex 6](#)
2. All immunisations will be recorded
3. See Study Procedures Manual (SPM)
4. See [Annex 5](#)
5. See Section [9.2.7.3.1](#)
6. For subjects not enrolled previously
7. Because of a possible overlap of studies EPI-MAL-002 and EPI-MAL-003, study conclusion of EPI-MAL-002 for children enrolled in enhanced hospitalisation surveillance will be done at start of study EPI-MAL-003 (as the RTS,S/AS01E vaccine becomes available in the sites that are exposed clusters).

(Amended 5 May 2020)

CONFIDENTIAL115055 (EPI-MALARIA-002 VS AME)
Protocol Amendment 7 Final**9.2.7.3. Biological sample handling and analysis****9.2.7.3.1. *Biological samples***

All enrolled subjects admitted to the hospital are expected to have routine laboratory tests performed according to good medical practice and routine practice (see Section 9.2.7.5), including, but not limited, to:

- All hospitalised children: haemoglobin concentration or full blood count
- Malaria suspects: Access to diagnosis of malaria using RDT and/or microscopy according to routine practice will be ensured for all children clinically suspected of malaria during active surveillance and at all the health care facilities.
- Meningitis suspects: CSF examination (and blood culture if feasible) according to routine practice (first line testing).
- Neurological diseases such as seizures, encephalitis, Acute Disseminated Encephalo-Myelitis (ADEM), Guillain Barre syndrome suspected: require neurological investigations (e.g. magnetic resonance imaging if available), eventually CSF analysis and other laboratory testing according to routine practice.
- Some AESI (such as diabetes mellitus, renal failure, hepatic failure, severe thrombocytopenia with bleeding) require laboratory testing for case management.

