9.7.7.2. Statistical approach

Incidence rates for each event will be calculated by dividing the number of cases by person-time as defined in [Table 8](#). Of note, for cerebral malaria, incidence following DTP/HepB/Hib vaccine or virtual vaccination will be derived and Time-to-Onset will be computed (see Section [9.7.5.2.1](#)).

CONFIDENTIAL

115055 (EPI-MALARIA-002 VS AME)
Protocol Amendment 7 Final

For analyses using detailed information from the eCRF, children whose parents do not consent for them to take part in the active surveillance groups will not be included in the denominator.

Table 8 Incidence rate and prevalence calculations for other objectives (children enrolled in active surveillance)

Endpoints	Numerator	Denominator
Any malaria	# cases of any malaria Source: Outpatient visits and hospitalisations at all health care facilities	Person-years contribution of enrolled children
Any P. falciparum malaria	# cases of any malaria due to P. falciparum Source: Outpatient visits and hospitalisations at all health care facilities	Person-years contribution of enrolled children
Severe malaria	# cases of severe malaria Source: Hospitalisations	Person-years contribution of enrolled children
Severe P. falciparum malaria	# cases of severe malaria due to P. falciparum Source: Hospitalisations	Person-years contribution of enrolled children
Cerebral malaria	# cases of cerebral malaria Source: Hospitalisations	Person-years contribution of enrolled children
Anaemia in hospitalised children	# cases of anaemia Source: Hospitalisations	Number of enrolled children
Death – all cause	# deaths (due to any cause) Source: Scheduled home visits; outpatient visits and hospitalisations at all health care facilities; completion visit; HDSS or equivalent surveillance system register	Person-years contribution of enrolled children
Malaria attributed deaths	# deaths with malaria listed as a contributing cause Source: Scheduled home visits; outpatient visits and hospitalisations at all health care facilities; completion visit; HDSS or equivalent surveillance system register	Person-years contribution of enrolled children
Hospitalisation - all cause	# of children hospitalised during study period Source: Hospitalisations	Person-years contribution of enrolled children

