#### **3.2. Secondary Objectives**

In children living in the study area, prior to implementation of RTS,S/AS01E:

- To estimate the incidence of aetiology confirmed, and/or probable meningitis (final classification).
- To estimate the incidence of probable meningitis (final classification).
- To estimate the incidence of aetiology confirmed, probable and/or clinically suspected meningitis (final classification).
- To monitor trends over time of meningitis cases identified at site level (first line laboratory).
- To describe risk factors for AESI, other AE leading to hospitalisation or death, meningitis and malaria.
- To describe the causes of hospitalisation (including AESI, other AE, meningitis and malaria).
- To describe the causes of death, overall and by gender.
- To assess the risk of febrile convulsions during the 7-day period and 1-month period following administration of routine EPI vaccines.

---

 Acute disseminated encephalomyelitis (ADEM), encephalitis, Guillain-Barre Syndrome, hypotonic hypo responsive episode (HHE), general convulsive seizure  
Intussusception, hepatic failure or renal insufficiency  
Juvenile chronic arthritis, Stevens-Johnson syndrome/toxic epidermal necrolysis, Henoch-Schonlein purpura, Kawasaki disease  
Diabetes mellitus type I, thrombocytopenia, anaphylaxis

- To estimate the incidence of any malaria (including *P. falciparum* malaria) diagnosed by rapid diagnostic test (RDT) and/or microscopy.
- To estimate the incidence of severe malaria (including *P. falciparum* malaria) diagnosed by RDT and/or microscopy.
- To estimate the incidence of cerebral malaria (malaria diagnosed by RDT and/or microscopy).
- To estimate the prevalence of anaemia among hospitalised children.
- To estimate the incidence of all-cause hospitalisations and hospitalisations attributed to malaria (including *P. falciparum*).
- To estimate the mortality rate (all-cause mortality and deaths attributed to malaria [including *P. falciparum*]), overall and by gender.

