### **4.2. Secondary endpoints**

As per protocol with more details.

In children living in the study area, prior to implementation of RTS,S/AS01E:

- Occurrence of probable meningitis (final classification).
- Occurrence of clinically suspected meningitis (final classification).
- Occurrence of meningitis cases identified at site level (first line laboratory):
- Occurrence of hospitalisation (including those attributed to an AESI, other AE, meningitis, or malaria) or death.
- Occurrence of febrile convulsions during the 7-day period (Days 0-6) and 1-month period (Days 0-29) following administration of routine EPI vaccine.
- Occurrence of two events used as surveillance quality indicators: abscess at injection site during the 7-day period (Days 0-6) following any routine vaccination and foot positional deformation.

In children included in AS, prior to implementation of RTS,S/AS01E:

- Occurrence of episodes of malaria diagnosed by RDT and/or microscopy
  - Any malaria
  - *P. falciparum* malaria
  - *P. vivax* or other Plasmodium species that cause malaria
  - Severe malaria
  - Severe *P. falciparum* malaria
  - Severe *P. vivax* malaria or other Plasmodium species that cause malaria
  - Cerebral malaria
  - Fatal malaria
  - Fatal *P. falciparum* malaria
- Occurrence of anaemia at hospital entry among hospitalised children
  - All anaemia
  - Severe anaemia
- Occurrence of hospitalisation
  - All causes
  - Hospitalisations for malaria (including *P. falciparum* malaria).
  - Hospitalisations for *P. falciparum* malaria
- Occurrence of death
  - All causes
  - Malaria attributed deaths
  - *P. falciparum* malaria attributed deaths
  - AE attributed deaths

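### Anaemia prevalence among hospitalised children is divided by all enrolled active-surveillance children, so the planned figure is anaemic admissions per enrolled child

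*SAP*

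**What the plan says.** The target is the same in both documents. SAP 3.2 gives the objective as "To estimate the prevalence of anaemia among hospitalised children", and SAP 4.2 gives the endpoint as "Occurrence of anaemia at hospital entry among hospitalised children". Protocol 8.2 and 9.3.2 agree.

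The calculation is in SAP 6.11.2: "The prevalence rate for anaemia will be computed by dividing the number of all cases by the number of enrolled children". Both anaemia rows of SAP Table 4 repeat it. The severe anaemia row, for example, has the numerator "cases of severe anaemia Source: Hospitalisations" and all enrolled children as denominator. Protocol Table 8 (9.7.7.2) uses the same construction, with "cases of anaemia Source: Hospitalisations" over enrolled children.

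The population is fixed in SAP 6.11: "These analyses will be performed only on children enrolled in the AS ATP cohort for each group (6-12 weeks and 5-17 months)". The title of Table 4 also limits it to active surveillance (AS).

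Haemoglobin comes only from admissions. Protocol 9.2.7.2.11 says that for hospitalised subjects the "measurement of haemoglobin concentration, if available, at hospital entry will be recorded in the eCRF". Protocol 9.2.7.3.1 lists the routine tests expected on admission, including "All hospitalised children: haemoglobin concentration or full blood count".

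The analysis window is less clear. SAP 6.11.1 includes anaemia among the endpoints analysed from dose 3 to one year later. The two anaemia rows are the only rows of Table 4 with no limit to the follow-up time. SAP Table 5 marks a prevalence for AS only, and a description for both AS and enhanced hospitalisation surveillance (EHS).

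**The concern.** A child in active surveillance who is never admitted adds one to the denominator but cannot be a case, because haemoglobin is taken only at hospital entry. The planned quantity therefore combines two things: how often enrolled children are admitted, and what share of those admitted are anaemic. The objective asks only for the second.

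Three consequences follow.

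- The number reported for this objective would not estimate it, for either anaemia or severe anaemia.
- It would differ between sites and age groups wherever admission rates or follow-up differ. Follow-up does differ: SAP 7.2.13 caps some children at 3 years of age or 24 months, and others at 5 years of age or 44 months.
- In the before/after comparison with EPI-MAL-003, a change in admissions would appear as a change in anaemia prevalence even if the share of admitted children with anaemia stayed constant.

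If every episode counts, the figure is also not a proportion, so the exact binomial interval that SAP 7.1 sets as default does not suit it.

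The same SAP section holds a smaller conflict. Its text counts all episodes for every Table 4 endpoint, but the three hospitalisation rows count children, as Protocol Table 8 does for its hospitalisation rows. Table 3 does not stop person-time at a first admission.

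**Working it through.** **What the wording fixes.** In every other row of Table 4, the enrolled children are all AS children contributing person-time. Nothing in 6.11.2 or Table 4 narrows the term for anaemia, so it includes children never admitted.

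**Formula.** Let N be the number enrolled, h the share hospitalised, r the admissions per hospitalised child, and p the share of admissions with haemoglobin below the cut-off. Assume for now that haemoglobin is measured at every admission.

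- Planned: N·h·r·p / N = h·r·p
- Target, per admission: N·h·r·p / (N·h·r) = p
- Planned divided by target: h·r

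The plan states no anaemia figure, so there is nothing to reproduce. The documents also give no h, r, p or admission rate. All inputs below are assumptions except N = 10,000 per age group (Protocol 9.5) and the window lengths.

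**Size at a true share of 50%**

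| h | r | h·r | Reported | Too low by a factor of |
|---|---|---|---|---|
| 0.10 | 1.0 | 0.10 | 5.0% | 10 |
| 0.10 | 1.5 | 0.15 | 7.5% | 6.7 |
| 0.30 | 1.0 | 0.30 | 15.0% | 3.3 |
| 0.30 | 1.5 | 0.45 | 22.5% | 2.2 |

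In counts, with N = 10,000, h = 0.20, r = 1.0 and p = 0.60, there are 2,000 admissions and 1,200 cases. The planned figure is 1,200/10,000 = 12%. The target is 1,200/2,000 = 60%.

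**Dependence on follow-up.** At a constant λ admissions per person-year over t years, the planned figure is p·λ·t. SAP 7.2.2 puts dose 3 at Month 2, and SAP 6.11.1 puts one and two years after dose 4 at Months 32 and 44. The windows are therefore 30 months (2.5 years) and 42 months (3.5 years). With p = 50%:

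| λ per PY | D3 to D3+1Y (t = 1) | D3 to D3+2Y (t = 2) | D3 to D4+1Y (t = 2.5) | D3 to D4+2Y (t = 3.5) |
|---|---|---|---|---|
| 0.05 | 2.5% | 5.0% | 6.3% | 8.8% |
| 0.10 | 5.0% | 10.0% | 12.5% | 17.5% |
| 0.30 | 15.0% | 30.0% | 37.5% | 52.5% |

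The last cell exceeds the true 50% because admissions per enrolled child pass one (0.30 × 3.5 = 1.05). So the figure is not always too low; it simply does not track p.

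**Missing haemoglobin.** In the 12% example, leaving 10% or 30% of admissions unmeasured lowers the planned figure to 0.12 × 0.9 = 10.8% or 0.12 × 0.7 = 8.4%. The share among those measured stays at 60%, provided missingness is unrelated to anaemia.

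**Hospitalisation rows.** Counting children once over full person-time understates the admission rate by 1 − (1 − e^(−λt))/(λt). At t = 1 this is 2.5% for λ = 0.05 and 13.6% for λ = 0.30. Under the all-episodes text it is zero.

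**The case against.** Five points can be made for the plan.

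- **The row label refers to hospitalised children, so the denominator may be shorthand.** That may have been the intention, but the sentence in 6.11.2 and the denominator cell say otherwise, and the other rows use the same term for all AS children.
- **A case is never defined as an admission.** This is fair. SAP 7.2.10 gives only cut-offs, and the de-duplication rules in 7.2.8 do not cover anaemia. The count of all cases, sourced from hospitalisations, favours admissions. If each child counted once, r would drop out and a true 50% of hospitalised children would be reported as 5–15% at h = 10–30%. The mismatch remains.
- **The information is not lost.** Table 5 describes anaemia in AS and in EHS, where every child is hospitalised, and Table 4 counts hospitalised AS children. An approximate share could be assembled from these outputs. That is true, but it is not the prevalence the plan defines.
- **A figure per enrolled child may serve the EPI-MAL-003 impact comparison**, since admission is itself something the vaccine may change. This supports keeping it as a separately labelled result, but not reporting it as prevalence in hospitalised children.
- **A denominator restricted to measured children may select.** Haemoglobin is recorded only where available, so the number unmeasured has to be reported.

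The endpoint is also secondary and descriptive. It is outside the interim analysis and every risk-factor model, which limits the consequences.

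**Conclusion.** The concern holds. As written, the AS prevalence of anaemia and severe anaemia does not estimate the stated secondary objective, and this conclusion needs no assumed number. Protocol Table 8 has the same fault, and SAP Section 9 does not mention it.

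The size rests wholly on assumed admission and anaemia shares. With 10–30% of children hospitalised and 1.0–1.5 admissions each, the figure is too low by a factor of about 2 to 10. At 0.10 admissions per person-year it rises from 5% to 17.5% between the one-year and 3.5-year windows, with the true share fixed at 50%. The follow-up calculation also assumes that anaemia is computed in each window, which the plan leaves unclear.

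This should be corrected before the final analysis, but no co-primary result depends on it. The hospitalisation conflict is minor: 2.5–14% in the one-year window if the Table 4 wording is followed, and SAP 6.10.5 already plans other hospitalisation rates.

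**What to change.** 1. For anaemia and severe anaemia, change the denominator in SAP 6.11.2 and Table 4 to one of two units: hospitalised AS children (first admission in the window), or admissions. In either case require haemoglobin recorded at entry.
2. Count the numerator in the same unit, and report the number without a measurement.
3. State the same window in 6.11.1, Table 4 and Table 5.
4. If the figure per enrolled child is wanted for the EPI-MAL-003 comparison, keep it as an extra row labelled as such.
5. For hospitalisation, state one rule: all admissions over full person-years, or first admissions with person-time stopped there.
6. Record both changes in SAP Section 9, since Protocol Table 8 carries the same anaemia denominator.

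The cost is SAP wording and a changed denominator. Admissions and entry haemoglobin are already in the eCRF. Because a haemoglobin test is expected for every hospitalised child, few results should be missing, and the reported count will show whether that is so. Protocol 9.3 aligns endpoints with EPI-MAL-003, so the same definitions must be used there; its SAP is not among the documents and could not be checked.

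### SAP 6.11.2 gives two numerators for hospitalisation incidence: all episodes in the text, children hospitalised in Table 4; if the table is programmed, the rate comes out low, and lower as the window lengthens

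*SAP*

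**What the plan says.** The objective in SAP 3.2 is event-based: "To estimate the incidence of all-cause hospitalisations and hospitalisations attributed to malaria".

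The text of SAP 6.11.2, which covers every endpoint in Table 4, follows it: "incidence rate will be calculated by dividing the number of all cases over the follow-up period by person-year as defined in the table". On repeats it adds: "If a subject had several cases during the period defined, all episodes will be reported".

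The hospitalisation rows of Table 4 differ. For all causes the numerator is the number "of children hospitalised during the follow-up time of each analysis Source: Hospitalisations". For malaria it is the number "of children hospitalised during the follow-up time of each analysis where malaria is listed as the primary diagnosis Source: Hospitalisations". The P. falciparum row has the same form. The malaria episode rows of the same table count cases. Protocol Table 8 (section 9.7.7.2) also counts children, as the number "of children hospitalised during study period", over person-years.

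The denominator is the same under either reading: "The number of person-years will be computed as the sum of subjects follow-up period expressed in years". The Table 3 stop dates are the end of the window, death, and "Date of last contact • Date of migration • Date when child reaches 5 years". The first admission is not among them. SAP Table 2, used for rates after each dose, does stop at the first event.

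**The concern.** Two programmers could each follow SAP 6.11.2 faithfully and produce different hospitalisation rates. One of the two results is also hard to interpret. Counting each child once calls for person-time that ends at the first admission; counting full person-time calls for every admission. Table 4 combined with Table 3 takes one half of each.

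SAP 6.11.1 says these windows are there to prepare the comparison with EPI-MAL-003. A child count over full person-time saturates as follow-up lengthens, and does so faster where admissions are more frequent. Rates from the 1-year, 2-year and Month 44 windows would then not be on one scale, and contrasts between sites or periods would be pulled towards the null.

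**Working it through.** The plan states no hospitalisation rate, precision or power for this endpoint, so there is no figure of its own to reproduce.

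**Direction, without assumptions.** Let C be children admitted at least once, A all admissions, P full person-time and F person-time to first admission (or to the end of follow-up if there is none). Then A ≥ C and F ≤ P, so C/P ≤ A/P and C/P ≤ C/F. The Table 4 figure C/P cannot exceed either coherent rate. It is strictly lower once any child is readmitted (against A/P) or has follow-up after a first admission (against C/F).

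**Growth with the window.** Against the first-admission rate, the ratio is F/P. With complete follow-up this is the average of the admission-free curve over the window. That curve never rises, so its average falls as the window lengthens, even if the rate changes with age.

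**Inputs for size.**
- Windows (SAP 6.11.1, visit months in SAP 7.2.2): D3 to D3+1Y = 1 year, the main analysis; D3 to D3+2Y = 2 years; D3 to D4+1Y = Month 2 to 32 = 2.5 years; D3 to D4+2Y = Month 2 to 44 = 3.5 years; D1 to D4+2Y = 44 months = 3.67 years.
- Admission rate r: an assumption. The only anchor is protocol 7.2, where 676 of 2,974 control children aged 5-17 months (22.7%) had at least one SAE over 20 months. This gives -ln(1 - 0.2273)/(20/12) = 0.155 per year, taken as 0.15. Range tried: 0.05 to 0.50.

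**Formula.** With a constant rate r and window T, C/P is (1 - exp(-rT))/T, while A/P and C/F both equal r. The shortfall is 1 - (1 - exp(-rT))/(rT). For r = 0.15 and T = 1: 1 - 0.1393/0.15 = 7.1%. For 44 months, rT = 0.55: 1 - 0.4231/0.55 = 23.1%.

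| r per year | 1 y | 2 y | 2.5 y | 3.5 y | 3.67 y |
|---|---|---|---|---|---|
| 0.05 | 2.5% | 4.8% | 6.0% | 8.3% | 8.6% |
| 0.10 | 4.8% | 9.4% | 11.5% | 15.6% | 16.3% |
| 0.15 | 7.1% | 13.6% | 16.6% | 22.2% | 23.1% |
| 0.30 | 13.6% | 24.8% | 29.6% | 38.1% | 39.4% |
| 0.50 | 21.3% | 36.8% | 42.9% | 52.8% | 54.2% |

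**Children who differ in risk.** With gamma frailty of shape 1 and mean 0.15, the ratio to the all-admission rate is 1/(1 + rT): 1/1.15 = 0.870 at 1 year and 1/1.55 = 0.645 at 44 months, shortfalls of 13.0% and 35.5%. Against the first-admission rate the ratio is ln(1 + rT)/(rT): 0.932 and 0.797, shortfalls of 6.8% and 20.3%.

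**Effect on a before/after ratio.** Take a true 20% reduction, from 0.15 to 0.12 per year, with the child count used in both studies. The ratio seen at 1 year is (1 - exp(-0.12))/(1 - exp(-0.15)) = 0.1131/0.1393 = 0.812 instead of 0.80. At 44 months it is (1 - exp(-0.44))/(1 - exp(-0.55)) = 0.3560/0.4231 = 0.841.

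**The case against.** The strongest reply is that the text governs. It is addressed to every Table 4 endpoint and says that all episodes count. Read that way, numerator and person-time match, Table 3 rightly has no stop at first admission, and nothing is biased. The mock tables and programming specifications that the SAP mentions are not among the documents and may already settle it. This stands as far as it goes: the firm defect is the contradiction, and the low rate follows only if the table rows are used. It does not remove the conflict, because the child-level wording is not an isolated slip. Protocol Table 8 repeats it, and protocol 9.2.5.7 and SAP 7.2.11 describe hospitalisation in terms of a subject.

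Second, coherent hospitalisation rates are planned elsewhere. SAP 6.10.5 and Table 5 include a rate after vaccination that stops at the first event, a rate in children under 5 that counts all events, and cumulative probabilities. So a reader might infer that the hospitalisation objective goes unanswered, and the documents do not support that. Those analyses use other windows, however, so they do not replace the ones here.

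Third, the large percentages belong to the additional windows; the main analysis is at 1 year. The anchor is first SAEs in another trial, not admissions in this population, and nothing in the documents supports 0.5 per year. Malaria-only admissions are necessarily rarer than all admissions. All of this stands.

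**Conclusion.** The point holds as a contradiction that should be resolved before the final tables are produced. If the three Table 4 rows are programmed as written, the result is below both a first-admission rate and an admission rate, and the gap widens with the window. If the text is followed, there is no bias.

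The size is conditional on an assumed constant rate of 0.15 admissions per person-year and no variation between children: about 7% in the main 1-year window (5 to 21% for 0.1 to 0.5), 14% at 2 years and 23% at 44 months. It is smaller for malaria-only admissions; at 0.05 per year, for example, 2.5% at 1 year. Variation between children enlarges the shortfall against the all-admission rate.

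Two stronger readings should be resisted. The documents do not show that the hospitalisation rates will be biased low, because they do not show which rule is programmed. Nor do they show serious damage to the comparison with EPI-MAL-003: protocol 9.3 aligns the endpoints of the two studies, and with the same definition and window in both, the illustrated ratio moves by about one percentage point at 1 year and four at 44 months.

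**What to change.** Choose one definition, write it in both the text and Table 4, and use the same one in EPI-MAL-003.

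- **Preferred, because it fits SAP 6.11.2 and the objective:** make the numerator of the all-cause, malaria and P. falciparum rows the number of hospitalisations. Two additions are needed. One is a counting rule that merges transfers and immediate readmissions into a single admission: an overnight stay at a primary facility counts as a hospitalisation (protocol 9.2.1.1), so an onward referral could count twice, and SAP 7.2.8 merges AESI, meningitis, other AE and malaria events but not all-cause admissions. The other is an interval that allows for repeat admissions within a child.
- **Alternative:** keep the child count, add the date of first admission (for the cause in question) to the Table 3 stop dates for these rows, and label the result a first-admission rate.

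Under the preferred option the departure from protocol Table 8 should be listed in SAP section 9, and the number of children hospitalised can still be shown as a plain count.

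The cost is a wording change, a small amount of programming and a somewhat wider interval. Under the shape-1 frailty used above, the variance of the count rises by a factor 1 + rT, so the interval widens by √1.15 = 1.07 at 1 year and √1.55 = 1.24 at 44 months.
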